6.3 Data Monitoring Committee

An independent, external DMC will be established for periodic review of unblinded safety data and to alert AbbVie to possible safety concerns related to the conduct of the study to ensure subject safety. The DMC will review safety data of the first 80 enrolled subjects through 8 weeks of treatment to determine if there are any significant safety concerns that would warrant any study action. Thereafter, the DMC will review safety data on a regular basis and as needed based on the accumulating safety data and will provide recommendations to AbbVie.

The DMC Charter will describe the roles and responsibilities of the DMC members, frequency of data reviews, and relevant data to be assessed. Communications from the DMC to the Study Team will not contain information that could potentially unblind the team to subject treatment assignments.

In addition, the DMC will conduct a futility analysis as described in Section 7.5.

6.4 Cardiovascular Adjudication Committee

An independent committee of physician experts in cardiovascular adjudication will be utilized to assess potential cardiovascular AEs in a blinded manner as defined by the Cardiovascular Adjudication Committee charter.

7 STATISTICAL METHODS & DETERMINATION OF SAMPLE SIZE

7.1 Statistical and Analytical Plans

An unblinded analysis for Period 1 will be conducted after all subjects have completed Week 52 or have prematurely discontinued the study prior to Week 52. An unblinded analysis for Period 2 will be conducted after all subjects have completed Week 104 or have prematurely discontinued the study prior to Week 104. Additional unblinded analysis in Period 2 may be conducted for regulatory purposes. To maintain integrity of the trial and avoid introduction of bias, study sites and subjects will remain blinded until all subjects have completed Period 2 (Week 104).

Statistical analyses will be described and fully documented in the Statistical Analysis Plan (SAP). The statistical analyses will be performed using SAS (SAS Institute Inc., Cary, North Carolina, USA).

7.2 Definition for Analysis Populations

The Full Analysis Set (FAS) will be defined for Period 1 and Period 2. The FAS population in Period 1 (FAS1) includes all randomized subjects who received at least 1 dose of study drug in Period 1. The FAS population in Period 2 (FAS2) is defined as all subjects who achieved remission for at least 24 consecutive weeks prior to the Week 52 Visit (at the end of Period 1) and received at least 1 dose of study drug in Period 2. In addition, an exploratory analysis set will be defined for Period 2 to include all subjects who did not meet these remission criteria (i.e., achieve remission for at least 24 weeks prior to the Week 52 Visit) but continued in Period 2 on their originally randomized treatment assignment. Primary efficacy analysis for primary and key secondary endpoints will be carried out on the FAS1 population in Period 1 and on the FAS2 population in Period 2. Exploratory efficacy analyses for Period 2 will be conducted for selected variables for the exploratory analysis set. Subjects will be grouped according to treatment as randomized.

The Per-Protocol Analysis Set will be defined to represent a subset of the FAS1 subjects without any major protocol violations during the study which are expected to impact the primary endpoint. Subjects to be excluded from the Per-Protocol Population will be identified before the Week 52 database lock. The Per-Protocol Population will be used to analyze the primary efficacy endpoint in a sensitivity analysis. Additional analyses may be conducted on the Per-Protocol Analysis Set in order to evaluate the impact of major protocol violations.

The Safety Analysis Set will be defined for Period 1 and Period 2. The Safety Analysis Set in Period 1 will consist of all subjects who received at least 1 dose of study drug in Period 1. The Safety Analysis Set in Period 2 will consist of all subjects who received at least 1 dose of study drug in Period 2. For the Safety

Analysis Set, subjects are assigned to a treatment group based on the treatment actually received, regardless of the randomized treatment.

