3.3 Secondary Endpoints

Multiplicity-controlled secondary endpoints include:

- 1. Proportion of subjects achieving sustained complete remission from Week 12 through Week 52. Sustained complete remission is defined as having achieved all of the following:
- Absence of GCA signs and symptoms from Week 12 through Week 52;
- Normalization of ESR (to < 30 mm/hr; if ESR ≥ 30 mm/hr and elevation is not attributable to GCA, this
 criterion can still be met) from Week 12 through Week 52;
- Normalization of hsCRP (to < 1 mg/dL without elevation [on 2 consecutive visits] to ≥ 1 mg/dL) from Week 12 through Week 52; and
- Adherence to the protocol-defined CS taper regimen.
- 2. Cumulative CS exposure through Week 52.
- 3. Time to first disease flare through Week 52. Disease flare is defined as an event determined by the investigator to represent recurrence of GCA signs or symptoms or an ESR measurement \geq 30 mm/hr (attributable to GCA) AND requiring an increase in CS dose.
- 4. Proportion of subjects who experience at least 1 disease flare through Week 52.
- 5. Proportion of subjects in complete remission at Week 52. Complete remission is defined as having achieved all of the following:
- · Absence of GCA signs and symptoms;
- Normalization of ESR (to < 30 mm/hr); if ESR ≥ 30 mm/hr and elevation is not attributable to GCA, this
 criterion can still be met.
- Normalization of hsCRP to < 1 mg/dL; and
- Adherence to the protocol-defined CS taper regimen.
- 6. Proportion of subjects in complete remission at Week 24.
- 7. Change from Baseline in the 36-item Short Form Quality of Life Questionnaire (SF-36) Physical Component Score (PCS) at Week 52.
- 8. A group of four endpoints:
- Number of disease flares per subject through Week 52;
- Change from Baseline in Functional Assessment of Chronic Illness Therapy-Fatigue (FACIT-Fatigue) at Week 52:
- Assessment of Treatment Satisfaction Questionnaire for Medication (TSQM) patient global satisfaction subscale at Week 52;
- Rate of CS-related AEs through Week 52

Additional Endpoints for Period 1 are:

Proportion of subjects in complete remission at Week 12

Change from Baseline in SF-36 by visit

Change from Baseline in FACIT-Fatigue by visit

Assessment of TSQM patient global satisfaction subscale by visit

Change from Baseline in EuroQoL Five Dimensions Five Levels Questionnaire (EQ-5D-5L) by visit

Assessment of Patients' Global Impression of Change (PGIC) by visit

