7.3 Statistical Analyses for Efficacy

Analysis of Primary and Key Secondary Endpoints in Period 1

For the global analysis, the overall type I error rate of the primary and ranked key secondary endpoints for the 2 upadacitinib doses will be strongly controlled using a graphical multiple testing procedure.

Specifically, the testing will utilize the endpoint sequence of primary endpoint followed by key secondary endpoints in the order as specified in Section 3.2 and Section 3.3. The testing will start with the primary endpoint of 15 mg QD with α = 0.05. Continued testing will follow a pre-specified α transfer path, which includes downstream transfer along the endpoint sequence within each dose as well as cross-dose transfer. The testing of 7.5 mg QD dose will start with transferred α if endpoint 7 in Section 3.3 of the 15 mg QD dose is significant. The group of endpoints labeled as 8 in Section 3.3 will be tested using the Hochberg procedure, conditional on significance of higher ranked endpoints. More details of the graphical procedure will be specified in the SAP. An alternative testing procedure will be done for the regulatory purposes in Japan. More details of the graphical procedure will be specified in the SAP. Unless otherwise specified, all statistical tests will be performed at a 2-sided significance level of 0.05.

The primary analysis will be conducted after all subjects have completed the Week 52 visit or have prematurely discontinued from the study prior to Week 52. For the primary efficacy endpoint, the upadacitinib groups will be compared with the PBO group using the Cochran-Mantel-Haenszel method adjusting for stratification factors. The primary approach for handling missing data will be Non-Responder Imputation incorporating multiple imputation (NRI-MI). Subjects with missing data will be counted as non-responders, except when missing at random can be reasonably assumed, which will be handled by multiple imputation. For example, missing due to COVID-19 logistical restriction or due to political conflict will be handled by multiple imputation. A sensitivity analysis will be performed based on As Observed analysis in which subjects with missing components of sustained remission at Week 52 will be excluded from analysis. Other key binary endpoints will be analyzed similarly.

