4.0 Analysis Populations

The following population sets will be used for the analyses.

- The Full Analysis Set (FAS) will be defined for Period 1 and Period 2.
 - The FAS in Period 1 (FAS1) consists of all randomized subjects who received at least 1 dose of study drug in Period 1.
 - The FAS in Period 2 (FAS2) consists of all subjects who achieved remission for at least 24 consecutive weeks prior to the Week 52 Visit (at the end of Period 1) and received at least 1 dose of study drug in Period 2.
- An exploratory analysis set (FAS2 E) is defined for Period 2 to include all subjects who had absence of GCA signs and symptoms AND were CS-free at the Week 52 visit, but did not achieve remission for at least 24 consecutive weeks prior to the Week 52 Visit, and continued and received at least 1 dose of study drug in Period 2 on their originally randomized treatment assignment.
- The Per-Protocol Analysis Set is defined to represent a subset of the FAS1 subjects without any major protocol violations during the study which are expected to impact the primary endpoint. The final criteria and the exclusion of subjects for the Per-Protocol Analysis Set will be finalized before the database lock for Primary Analysis. The Per-Protocol Analysis Set will be used to analyze the primary efficacy endpoint as a supplementary analysis.
- The Safety Analysis Set in Period 1 (SS1) consists of all subjects who received at least 1 dose of study drug in Period 1.
- The Safety Analysis Set in Period 2 (SS2) consists of all subjects who received at least 1 dose of study drug in Period 2.
- The Long-Term Safety Analysis Set (SS LT) consists of all subjects who received at least one dose of study drug in Period 1 and received the same study drug in Period 2.

Primary efficacy analysis for primary and multiplicity-controlled secondary endpoints will be carried out on FAS1 and SS1 (for the endpoint of rate of CS-related AEs) in Period 1. Efficacy analysis for additional endpoints in Period 1 will be carried out on FAS1, and efficacy analysis for additional endpoints in Period 2 will be carried out on FAS2.

Exploratory efficacy analyses for Period 2 will be conducted for additional endpoints in Period 2 on FAS2 E. For all efficacy analyses, subjects will be grouped according to treatment (or treatment sequence) as randomized.

For Safety Analysis Sets, subjects are assigned to a treatment group based on the treatment actually received, regardless of the treatment randomized.

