12.0 Overall Type-I Error Control

The overall Type I error rate of the primary and the multiplicity-controlled secondary endpoints will be strongly controlled using a graphical multiplicity adjustment method.^{3,4}

Specifically, the primary and multiplicity-controlled secondary endpoints as specified in Section 3.1 and Section 3.2 will be tested in the order as specified below and will begin with testing the primary endpoint for upadacitinib 15 mg dose using α of 0.05. Continued testing will follow a pre-specified α transfer path which includes downstream transfer along the endpoint sequence within each dose as well as cross-dose transfer. Adjusted P values for the primary and multiplicity-controlled secondary endpoints will be provided based on the testing procedure.

The testing procedures are provided below in Figure 2 (for US/FDA regulatory purpose) and Figure 3 (for PMDA regulatory purpose). The arrows specify the α transfer paths. Once a null hypothesis of an endpoint is rejected (i.e., deemed significant) at its assigned significance level, its significance level will be transferred to subsequent endpoint(s) following the arrow(s). The numbers on the arrows denote the weights for transferring and (possibly) splitting significance levels. Specifically, the weight 1 and 1/2 denotes 100% and 50% transfer of significance level, respectively. The primary and multiplicity-controlled secondary endpoints (V1-V7 in Table 3) will be tested sequentially. The remaining multiplicity-controlled secondary endpoints will be grouped together (V8-H in Table 3) and tested using Hochberg procedure.

[figure not shown]

Table 3. List of Primary and Secondary Endpoints for Regulatory Purpose (FAS1)

Name	Variable			
V0	Proportion of subjects achieving sustained remission at Week 52			
V1	Proportion of subjects achieving sustained complete remission from Week 12 through Week 52			
V2	Cumulative CS exposure through Week 52			
V3	Time to first disease flare through Week 52			
V4	Proportion of subjects who experience at least 1 disease flare through Week 52			
V5	Proportion of subjects in complete remission at Week 52			
V6	Proportion of subjects in complete remission at Week 24			
V7	Change from Baseline in the 36-item Short Form Quality of Life Questionnaire (SF-36) Physical Component Score (PCS) at Week 52			

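### The documents give conflicting analysis sets and grouping rules for one multiplicity-controlled endpoint, the rate of CS-related AEs through Week 52

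*Protocol*

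**What the plan says.** Protocol 3.3 lists "Rate of CS-related AEs through Week 52" in its eighth and last-ranked group of multiplicity-controlled endpoints. Protocol 7.3 makes this a confirmatory test: "The group of endpoints labeled as 8 in Section 3.3 will be tested using the Hochberg procedure", conditional on the higher-ranked endpoints.

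On the analysis set, Protocol 7.2 says "Primary efficacy analysis for primary and key secondary endpoints will be carried out on the FAS1 population in Period 1" and then "Subjects will be grouped according to treatment as randomized". SAP 9.1 puts all Period 1 efficacy analyses on FAS1. SAP Table 3, which defines the confirmatory family and includes this endpoint in V8-H, is headed "List of Primary and Secondary Endpoints for Regulatory Purpose (FAS1").

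SAP 4.0 differs. It says the analyses of the primary and multiplicity-controlled secondary endpoints "will be carried out on FAS1 and SS1 (for the endpoint of rate of CS-related AEs) in Period 1", and SAP 8.0 repeats that exception. For safety sets, SAP 4.0 adds that "subjects are assigned to a treatment group based on the treatment actually received, regardless of the treatment randomized". The same section also says that efficacy analyses, without exception, are grouped by randomised treatment, and SAP 8.0 describes the CS-related AE rate as a secondary efficacy endpoint.

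**The concern.** Two questions have two answers each: which set this endpoint is analysed on, and how subjects are grouped within it. The second matters more. If the safety-set rule applies, the groups being compared can depend on what was dispensed after randomisation, and the p-value is no longer strictly a test between randomised groups.

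That would pass without comment in a descriptive safety table. Here the p-value enters a procedure for which SAP 12.0 claims strong control of the type I error rate. Hochberg also works from the largest p-value in the group downwards. A change in this result can therefore alter the decisions on the flare count, FACIT-Fatigue and TSQM satisfaction.

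**Working it through.** **Plan's own figure.** The plan gives no rate, effect or power for this endpoint. Its one power statement concerns the primary endpoint: at least 90% for 60% v 40%, 210 v 105 subjects, Fisher's exact test, two-sided 0.05. Exact enumeration gives 91.0%, so it reproduces, and the present point does not affect it.

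**Passages side by side, for this endpoint.**

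| Place | Set | Grouping |
|---|---|---|
| Protocol 7.2 | FAS1 | as randomised |
| SAP 9.1 | FAS1 | not stated there |
| SAP Table 3 heading | FAS1 | not stated there |
| SAP 4.0, sentence on endpoints | SS1 | not stated there |
| SAP 8.0 | SS1 | not stated there |
| SAP 4.0, rule for efficacy analyses | – | as randomised |
| SAP 4.0, rule for safety sets | – | as received |

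Both SAP 4.0 rules can claim this endpoint: it is labelled an efficacy endpoint and is assigned to a safety set. Nothing says which rule prevails.

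**Membership.** FAS1 is everyone randomised who took at least one dose in Period 1. SS1 is everyone who took at least one dose in Period 1. They would differ only through someone dosed without being randomised, so they hold essentially the same people. Choosing between them changes, in effect, only the grouping.

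**Hochberg.** With four endpoints and group level α, the largest p-value is compared with α, then the next with α/2, α/3 and α/4. For α = 0.05 the cut-offs are 0.05, 0.025, 0.0167 and 0.0125. If a half-weight arrow leaves the group 0.025, they are 0.025, 0.0125, 0.0083 and 0.00625. The share reaching the group is set by the transfer paths in SAP Figures 2 and 3. If the CS-related AE p-value is the largest and is at or below α, all four hypotheses are rejected. If it is just above, the other three face stricter cut-offs.

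**Size.** Rate ratio = (events ÷ subject-years, 15 mg) ÷ (events ÷ subject-years, placebo). Suppose one event per subject-year in both arms and one year each. Moving two average placebo subjects to 15 mg gives (105 − 2)/(105 − 2) = 1.00 and (210 + 2)/(210 + 2) = 1.00, a ratio of 1.00 as before.

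To allow for chance, both groupings were simulated on assumed inputs: placebo rate 1.0 per year, rate ratio 0.7, between-subject gamma dispersion 1, 210 v 105 subjects, one year each, and outcomes following the treatment received. There were 4000 trials per setting. The test was on the log rate ratio at 0.05, with variance s₁²/(n₁m₁²) + s₀²/(n₀m₀²), where m and s² are each group's mean and variance of counts.

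| Misdosed | Direction | Average ratio, as randomised → as received | Trials where significance differs |
|---|---|---|---|
| 0 | either | identical | 0% |
| 1 | placebo subject took 15 mg | 0.703 → 0.701 | 3.2% |
| 1 | 15 mg subject took placebo | 0.703 → 0.702 | 4.1% |
| 2 | placebo subjects took 15 mg | 0.708 → 0.703 | 4.2% |
| 2 | 15 mg subjects took placebo | 0.703 → 0.700 | 5.6% |
| 5 | placebo subjects took 15 mg | 0.715 → 0.706 | 8.4% |
| 5 | 15 mg subjects took placebo | 0.713 → 0.706 | 8.8% |

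In every setting 49% to 55% of trials were significant, so many results lay near the cut-off, where disagreement is most likely.

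**The case against.** The best defence is that SS1 was chosen on purpose. Protocol 7.1 leaves full documentation of the analyses to the SAP, and the SAP names the exception twice, so the specific statement could override the general FAS1 sentences. The endpoint counts treatment-emergent events that the investigator relates to prednisone or prednisolone, with study drug exposure as the offset, and a safety set is a recognised choice for such a rate. On this view only a table heading and a general sentence were left unadjusted. The defence explains the choice of set. It does not settle the grouping, and it does not remove the conflict with Protocol 7.2.

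Some stronger readings are tempting but not supported:

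- A reader might infer that the SAP has fixed the grouping as treatment received. It has not. The efficacy rule in SAP 4.0 permits SS1 membership with randomised groups, and under that reading the consequence disappears.
- A reader might take Table 3 itself to require randomised grouping. Its heading says only FAS1; the grouping comes from Protocol 7.2 and SAP 4.0.
- A reader might expect a sizeable shift in the rate ratio. One can be produced by moving a few subjects with many events, but it then reflects the subjects picked.
- A reader might add that the as-received group is unclear for someone given the right tablet and the wrong steroid taper. The SAP states no rule for that case. However, kits are assigned by the interactive response system, and nothing shows that such errors occurred.

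**Conclusion.** The inconsistency is real and the consequence is minor. One multiplicity-controlled endpoint has two analysis sets and two grouping rules, and one combination lets a confirmatory comparison depart from the randomised groups.

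The numerical effect is nil if nobody is counted under another treatment. SAP 7.3 foresees wrong treatment as a deviation category, but the documents give neither a count nor a CS-related AE rate, so the simulated figures rest wholly on assumption. They suggest a negligible shift in the estimate and an occasional change in significance when the result is near its cut-off.

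The primary endpoint and ranked secondary endpoints 1 to 7 for the same dose are tested before this group and are not affected. A reader should not infer that the main efficacy conclusion or the sample size is in doubt.

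**What to change.** In SAP 4.0 and 8.0, specify FAS1 grouped as randomised for the multiplicity-controlled test of the CS-related AE rate. This agrees with Protocol 7.2, SAP 9.1 and Table 3, none of which then needs to change. Keep the SS1 version, grouped by treatment received, as a supportive safety summary.

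The cost is two SAP sentences. Because the sets have essentially the same members, no data are lost. No new data are needed and no power figure changes. The wording is best settled before the sponsor is unblinded for the Week 52 analysis, so that the grouping cannot appear to have been chosen afterwards.

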7.3 Statistical Analyses for Efficacy

Analysis of Primary and Key Secondary Endpoints in Period 1

For the global analysis, the overall type I error rate of the primary and ranked key secondary endpoints for the 2 upadacitinib doses will be strongly controlled using a graphical multiple testing procedure.

Specifically, the testing will utilize the endpoint sequence of primary endpoint followed by key secondary endpoints in the order as specified in Section 3.2 and Section 3.3. The testing will start with the primary endpoint of 15 mg QD with α = 0.05. Continued testing will follow a pre-specified α transfer path, which includes downstream transfer along the endpoint sequence within each dose as well as cross-dose transfer. The testing of 7.5 mg QD dose will start with transferred α if endpoint 7 in Section 3.3 of the 15 mg QD dose is significant. The group of endpoints labeled as 8 in Section 3.3 will be tested using the Hochberg procedure, conditional on significance of higher ranked endpoints. More details of the graphical procedure will be specified in the SAP. An alternative testing procedure will be done for the regulatory purposes in Japan. More details of the graphical procedure will be specified in the SAP. Unless otherwise specified, all statistical tests will be performed at a 2-sided significance level of 0.05.

The primary analysis will be conducted after all subjects have completed the Week 52 visit or have prematurely discontinued from the study prior to Week 52. For the primary efficacy endpoint, the upadacitinib groups will be compared with the PBO group using the Cochran-Mantel-Haenszel method adjusting for stratification factors. The primary approach for handling missing data will be Non-Responder Imputation incorporating multiple imputation (NRI-MI). Subjects with missing data will be counted as non-responders, except when missing at random can be reasonably assumed, which will be handled by multiple imputation. For example, missing due to COVID-19 logistical restriction or due to political conflict will be handled by multiple imputation. A sensitivity analysis will be performed based on As Observed analysis in which subjects with missing components of sustained remission at Week 52 will be excluded from analysis. Other key binary endpoints will be analyzed similarly.

For continuous change from baseline endpoints such as change from baseline in SF-36, PGA, EQ-5D-5L and FACIT-Fatigue, comparisons between the upadacitinib treatment groups and the PBO group will be carried out using the Mixed-Effect Model Repeat Measurement (MMRM) model with treatment group, visit, treatment-by-visit interaction, and stratification factors as the fixed factors and the corresponding baseline values as the covariates. TSQM, PGIC value will be analyzed using an MMRM model with treatment group, visit, treatment-by-visit interaction and stratification factors as the fixed factors. For cumulative CS dose, comparisons between the upadacitinib treatment group and the PBO group will be analyzed using a van Elteren test stratified by stratification factors. The median total cumulative prednisone dose over the 52 weeks for each treatment group and the corresponding 95% CI for the median will be presented.

For time-to-event endpoints, median time-to-event will be reported for each treatment group. Comparisons between the upadacitinib group and the PBO group will be conducted using stratified log

rank test; additional analyses may be conducted using Cox's regression to include baseline values and stratification factors as covariates.

For count endpoints, comparisons between the upadacitinib treatment group and the PBO group will be carried out using Poisson regression model with treatment group and stratification factors as covariates, adjusting for exposure duration.

Other Efficacy Variables

Additional efficacy variables are listed in Section 3.3 and will be summarized for Period 1 and 2. For all the additional efficacy variables in Period 1, the summary statistics and the statistical method will be the same as the corresponding variables described in the primary and key secondary analyses. For all the additional efficacy variables in Period 2, descriptive statistics will be provided for each treatment group sequence. For binary endpoints, frequencies and percentage with 95% CI using normal approximation will be reported for each treatment group and 95% CI will be reported for treatment difference. For continuous endpoints, the mean, standard deviation, 95% CI, median, and range will be reported for each treatment group and 95% CI will be reported for treatment difference. For time-to-event endpoints, median time-to-event will be reported for each treatment group. For count endpoints, the exposure duration adjusted event rates will be reported for each treatment group.

Sample Size Estimation

The planned total sample size of 420 subjects with a 2:1:1 ratio (upadacitinib 15 mg QD: upadacitinib 7.5 mg QD: PBO QD) was determined to have at least 90% power to detect a 20% difference in sustained remission rate at Week 52 between the upadacitinib 15 mg arm and the PBO arm (assuming a response rate of 40% in the PBO arm), using Fisher's exact test, with an overall two-sided alpha = 0.05.

